3.2.3 Efficacy Variables

Not Applicable

3.2.4 Pharmacodynamic Variables

Not Applicable

3.2.5 Immunogenicity Variables

Not Applicable

3.2.6 Exploratory Variables

The following exploratory disease activity parameters for RA will be assessed on day 1 and day 7:

- American College of Rheumatology (ACR) 20/50/70 response criteria
- Disease activity score 28 (DAS28)
- Clinical disease activity index (CDAI)
- Simplified disease activity index (SDAI)

The following exploratory biomarkers will be assessed:

- Matrix metalloproteinase-3 (MMP-3)
- Granulocyte macrophage colony-stimulating factor (GM-CSF)
- C-X-C motif chemokine ligand 10 (CXCL10)
- C-C motif chemokine ligand 2 (CCL2)
- Cartilage oligomeric matrix protein (COMP)
- Tumor necrosis factor (TNF)-alpha
- TNF-R1
- Interleukin-6 (IL-6)

4 STATISTICAL METHODS

4.1 Data Quality Assurance

All tables, figures, and data listings to be included in the report will be independently checked for consistency, integrity, and in accordance with

4.2 General Presentation Considerations

This section is not applicable to PK data.

4.2.1 Treatment

Cohort 1: 10 mg TCK-276 Cohort 2: 25 mg TCK-276

Cohort 3: 75 mg TCK-276

Cohort 4: 175 mg TCK-276

Pooled Placebo

Dose Group	Treatment Assignment	
1	10 mg TCK-276 (N = 6)	Placebo ($N = 2$)
2	25 mg TCK-276 (N = 6)	Placebo ($N = 2$)
3	75 mg TCK-276 (N = 6)	Placebo ($N = 2$)
4	175 mg TCK-276 (N = 6)	Placebo ($N = 2$)

4.2.2 Study Day

Study days will be numbered relative to the first day of study drug administration.

• If the date of event is before the study drug administration, then:

Study day = (Date of measurement – Date of study drug administration [i.e. Day 1])

• If the date of event is on or after the study drug administration, then:

Study day = (Date of measurement – Date of study drug administration [i.e. Day 1]) + 1

4.2.3 End of Study

The end of the study is defined as the date of the last visit of the last patient in the study or last scheduled procedure shown in the Table 6-1 Schedule of Assessments.

A patient is considered to have completed the study if he/she has completed all periods of the study including the last visit.

4.2.4 Baseline

Baseline value is defined as the last non-missing observation before the first administration of study drug.

No imputation will be done for missing baseline value for derivation of change from baseline or summary tables and shift tables.

4.2.5 Controlled, Repeat, Retest, Scheduled and Unscheduled Assessment

Repeat, retest, and unscheduled assessment will not be considered for the calculation of summary statistics and figures, unless assessment qualifies as baseline.

Average of controlled and planned (scheduled) assessment will be considered for the calculation of summary statistics and figures, if more than one controlled/planned assessment will be performed at a specific time point.

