4.2.6 Summary and Representation of Data

Continuous data will be summarized by cohort and treatment group using descriptive statistics (number, mean, standard deviation, minimum, median, and maximum).

Categorical data will be summarized by cohort and treatment group using frequency tables (number and percentage.

The minimum and maximum will be reported to the same number of decimal places as the raw data recorded in the database. The mean and median will be reported to one more decimal place than the raw data recorded in the database. The SD will be reported to two more decimal places than the raw data recorded in the database. In general, the maximum number of decimal places reported shall be four for any summary statistics.

Percentages will be presented to one decimal place for safety outputs and two decimal places for exploratory outputs. Percentages will not be presented for zero counts. Percentages will be calculated using N as the denominator. If sample sizes are small, the data displays will show the percentages, but any textual report will describe frequencies only. Percentage will be presented as whole number if count is 100.

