4.13.5 ECG

Standard safety 12-lead ECGs will be performed as shown in the section 6.1.

The following ECG parameters will be recorded:

PR interval (msec)

QRS interval (msec)

RR interval (msec)

QT interval (msec)

QT interval corrected using the Fridericia correction formula (QTcF) (msec).

The ECG will be evaluated by the Investigator as 'Normal', 'Abnormal, NCS' or 'Abnormal, CS'.

All ECG parameters will be listed by each patient and time point including changes from baseline.

Baseline is defined in section 4.2.4.

Descriptive statistics for observed values and changes from baseline will be presented by cohort and treatment group. A categorical QTc analysis will also be performed.

Measurements obtained at Screening will not be included in the shift tables and in the tabulations of descriptive statistics.

Measurements obtained prior to dosing in each period will be included in the tabulations for the treatment received in that specific treatment period.

A summary of the number and percentage of patients with QT/QTc intervals exceeding some predefined upper limits (eg, >450 msec, >480 msec, >500 msec for measured values as well as. >30 msec, >60 msec for changes from baseline) of ECG parameters (QT interval, QTcF and QTcB) will be displayed in a frequency table.

The listing of ECG abnormality will be presented separately.

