6.4 ECG Notable Criteria

ECG Parameters	Definition/threshold
	New value <= 450 msec
QT, QTcF	New value of > 450 msec and \leq 480 msec
	New value of > 480 msec and ≤ 500 msec
	New value of > 500 msec
	Increase from baseline <= 30 msec
	Increase from baseline of > 30 msec to ≤ 60 msec
	Increase from baseline of > 60 msec

QTcF = QT corrected using Fridericia's formula

Approval Signatures

Document Name: Statistical Analysis Plan 12 Sep 2023 TCK-276-102

System Version Number: 2 .0

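### The SAP does not say which post-dose ECGs enter the QT/QTcF threshold table; if its rule on unscheduled records is applied there, a patient who crosses a limit only on a triggered ECG goes uncounted

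*SAP*

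**What the plan says.** SAP 4.2.5 sets the rule for extra records: "Repeat, retest, and unscheduled assessment will not be considered for the calculation of summary statistics and figures, unless assessment qualifies as baseline". Baseline is the only exception inside the rule. The parent section, SAP 4.2, makes one exemption: "This section is not applicable to PK data". Safety ECG data are therefore not exempt.

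SAP 4.13.5 plans "A summary of the number and percentage of patients with QT/QTc intervals exceeding some predefined upper limits". It gives five example limits, ">450 msec, >480 msec, >500 msec for measured values as well as. >30 msec, >60 msec for changes from baseline", and says that the result "will be displayed in a frequency table". SAP 6.4 gives mutually exclusive bands for QT and QTcF, the highest change band being "Increase from baseline of > 60 msec". The absolute bands above 450 ms, like the one at or below it, are worded as new values. Neither section names the visits or record types used, or says that each patient is classified by the worst post-dose value.

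The protocol itself generates extra ECGs. Section 8.3.4 requires a 12-lead ECG after a clinically significant telemetry change, then hourly repeats until the event resolves or the patient is stable.

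**The concern.** Leaving unscheduled records out is sensible for means by time point, where they have no nominal time and would give some patients extra weight. A count of patients who ever exceeded a limit asks a different question. A triggered tracing is taken because something was seen, so leaving it out of such a count can only lower the cumulative figures.

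The rule is also one-sided. An unscheduled pre-dose ECG may become the baseline, but under 4.2.5 an unscheduled post-dose ECG might not count as a crossing.

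Safety is the primary objective, QTcF is a named endpoint, and this table is the patient count for QT prolongation. Two programmers could produce different counts from the same data, and both could cite the SAP.

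**Working it through.** **1. Does 4.2.5 reach the table?** The text points both ways.

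- Towards yes: SAP 4.2.6 says "Categorical data will be summarized by cohort and treatment group using frequency tables", and 4.13.5 calls the QT output a summary shown in a frequency table. A frequency table is thus a form of summary in this SAP.
- Towards no: 4.2.5 says *summary statistics*. SAP 4.2.6 uses that phrase when setting decimals for minimum, maximum, mean, median and SD, and treats percentages in a separate paragraph. SAP 4.12.1 (PK concentrations) and 4.15 (biomarkers) also use it for numeric descriptives.

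On either reading, the post-dose records behind the table are not stated.

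**2. Can a crossing appear only on an extra tracing?** The protocol's Schedule of Activities puts planned ECGs at baseline and at 1, 2, 4 and 8 h after dosing on Days 1 and 7, with further ECGs on Days 8, 9, 10 and 14. Telemetry on Days 1 and 7 runs until 12 h after dosing. A triggered ECG between 8 and 12 h therefore has no planned ECG at the same time, and a brief crossing then could be missed by every planned record.

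**3. What does one omitted patient change?** Each cohort has 6 active and 2 placebo patients, and SAP 4.13 pools placebo. The denominators are 6 per dose, 4 × 6 = 24 active and 4 × 2 = 8 placebo. The intervals are exact (Clopper-Pearson) 95%. For x = 0 the upper limit is 1 − 0.025^(1/n); for n = 6 this is 1 − 0.541 = 45.9%. For x = 1 the lower limit is 1 − 0.975^(1/n), and the upper limit solves (1 − p)^n + np(1 − p)^(n−1) = 0.025.

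| Group | Crossing counted | Crossing omitted |
|---|---|---|
| One dose | 1/6 = 16.7% (0.4 to 64.1%) | 0/6 = 0% (0 to 45.9%) |
| Pooled placebo | 1/8 = 12.5% (0.3 to 52.7%) | 0/8 = 0% (0 to 36.9%) |
| All active | 1/24 = 4.2% (0.1 to 21.1%) | 0/24 = 0% (0 to 14.2%) |

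The intervals overlap widely. What changes is whether the table reports a case at all.

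**4. Illustration with assumed values.** Baseline QTcF is 430 ms, the highest planned ECG 448 ms and a triggered ECG 485 ms.

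- Planned records only: 448 − 430 = 18 ms. None of the five limits in 4.13.5 is crossed; the 6.4 bands are at most 450 ms and a rise of at most 30 ms.
- All records: 485 − 430 = 55 ms. Three of five limits are crossed (>450, >480 and >30 ms); the 6.4 bands are >480 to 500 ms and a rise of >30 to 60 ms.

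In 6.4 the patient is not lost but moves down, so a lower band is overcounted.

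**5. Do other rules cover the gap?** Protocol 7.1.1 and 7.2 have QTcF criteria at about 500 ms and at a rise above 60 ms. These match 2 of the 5 limits. The other three (>450, >480 and >30 ms), and uncorrected QT, have no matching criterion. In the illustration, 485 < 500 and 55 < 60, so no QTcF value criterion is met.

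**The case against.** The strongest reply is that 4.2.5 was never meant for this table. Its phrase is used elsewhere for numeric descriptives, its second sentence concerns averaging at a time point, and 4.13.5 counts patients without restricting record type. That reading is tenable. It removes the exclusion but leaves the record set unstated. Table shells, which SAP 4.13.1 mentions, might settle it, but they are not part of these documents.

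The route is also narrow, and this stands. Telemetry assesses rate and rhythm, only a clinically significant change triggers an ECG, and the patient must cross a limit on that tracing and on no planned one. A reader might extend the concern to Days 2 to 6, but no telemetry is scheduled on those days, apart from hourly repeats that run on from Day 1.

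The value remains visible, and this stands too. SAP 4.13.5 says "All ECG parameters will be listed by each patient and time point including changes from baseline" and adds a separate listing of abnormalities. A clinically significant ECG finding meets the protocol's AE definition, and the largest crossings can surface through protocol 7.1.1 and 7.2 and the disposition output. With 6 patients per dose, a reader can count from the listing. One limit on these back-ups is that Day 7 is the last dose, so a later crossing cannot appear as a TEAE leading to discontinuation of study treatment.

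There are no hypotheses, and escalation rests on the Safety Review Committee's review of the data, not on this table. A planned-ECG-only table also gives patients more equal chances to cross. That would be a legitimate choice if stated and labelled.

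Finally, a bare worst-value rule would have its own flaw. Exclusion criterion 13 admits women with QTcF up to 470 ms, so a value above 450 ms may already be present at baseline. The fix must respect this.

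**Conclusion.** The point holds as an unresolved analysis rule: the SAP states an exclusion, does not say whether it applies to the QT/QTcF threshold table, and defines no post-dose record set for that table. If the exclusion is applied, a crossing seen only on a triggered or repeat ECG is undercounted in 4.13.5 and banded too low in 6.4. One patient makes the difference between 1/6 and 0/6 in a dose group.

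A reader might infer that the SAP plainly bars triggered ECGs from the table, or that a QT signal would be hidden. The documents support neither. The wording allows both readings, and the values stay in the listings and, if clinically significant, in the AE tables. Nor can the chance of an omission be calculated, because no rate of such crossings is given; the millisecond values above are assumed. The harm is limited to an undercount, or a count that disagrees with the listing. I rate it minor to should-fix, with medium confidence.

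**What to change.** - In SAP 4.2.5, limit the exclusion to by-time-point descriptive statistics and mean plots.
- In SAP 4.13.5 and 6.4, state that the QT and QTcF categories use each patient's worst valid post-dose value over all scheduled, repeat and unscheduled ECGs.
- Keep the new-value condition of 6.4: an absolute band counts as new only if the baseline was not already in that band or a higher one.
- Exclude technically invalid tracings under a stated rule, and footnote that patients with more tracings have more chances to cross a limit.

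The cost is a few lines of text and a small programming change, with no new data. SAP section 1 already provides a modification form for changes after finalization. The downsides are slightly less favourable counts, unequal numbers of tracings per patient, and the need to write the validity rule.

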4.2.6 Summary and Representation of Data

Continuous data will be summarized by cohort and treatment group using descriptive statistics (number, mean, standard deviation, minimum, median, and maximum).

Categorical data will be summarized by cohort and treatment group using frequency tables (number and percentage.

The minimum and maximum will be reported to the same number of decimal places as the raw data recorded in the database. The mean and median will be reported to one more decimal place than the raw data recorded in the database. The SD will be reported to two more decimal places than the raw data recorded in the database. In general, the maximum number of decimal places reported shall be four for any summary statistics.

Percentages will be presented to one decimal place for safety outputs and two decimal places for exploratory outputs. Percentages will not be presented for zero counts. Percentages will be calculated using N as the denominator. If sample sizes are small, the data displays will show the percentages, but any textual report will describe frequencies only. Percentage will be presented as whole number if count is 100.

4.2.7 On-treatment assessment/event

The overall observation period will be divided into three mutually exclusive segments:

1. pre-treatment period: from day of patient's informed consent to before date of admission

- 2. *on-treatment period*: from date of admission (Day -1) to discharge from site (11 days i.e., from Day -1 to Day 10)
- 3. *post-treatment period*: from after date of discharge from the Site up to follow-up/End of treatment visit. (7 days after the last dose)

4.3 Software

All report outputs will be produced using SAS[®] version 9.4 or later in a secure and validated environment.

The PK analyses will be conducted using Phoenix[®] WinNonlin (WNL) version 8.3 or later in a secure and validated environment.

All report outputs will be provided to the Sponsor in Microsoft Word document/RTF format.

4.4 Study Patients

4.4.1 Analysis Sets

Randomized Population (RAN): All patients that signed informed consent form and assigned randomization number.

Safety Population (SAF): All randomized patients who received at least one dose of study drug (active/placebo).

PK Population (PKAS): All randomized patients with at least one quantifiable TCK-276 concentration.

Exploratory population: All randomized patients who received at least one dose of study drug (active/placebo) and have at least one of the evaluable exploratory assessment data.

A summary table with the number of patients in each of the analysis population will be provided and this table will be displayed by cohort/treatment group and overall, for randomized population. A listing of patients excluded from analysis population will also be provided including reason of exclusion for randomized population.

4.4.2 Disposition of Patients

A clear accounting of the disposition of all patients who enter the study will be provided, from randomization to study and treatment completion.

Patient disposition will be summarized and will include the following information: number of patients randomized and dosed, number and percentage of patients completing the study and treatment, and the number and percentage of patients who were withdrawn (including reasons for withdrawal) from study and treatment. Disposition data will be presented based on RAN.

A by-patient listing of randomizations will be presented and include the following: each patient's randomization number, site, the treatment to which the patient has been randomized.

A by-patient listing of study and treatment discontinuation will be presented for the RAN. The listing will include the date of study exit, duration of treatment and reason for study treatment discontinuation.

A by-patient listing of informed consent response will be provided.

4.4.3 **Protocol Deviations**

All protocol deviations are predefined in the separate document, Protocol Deviation Specification.

4.4.3.1 Protocol Deviations with Non-PK Implications

The defined protocol deviations will be collected during the study period by site monitor/clinical team and programming team. All deviations related to study inclusion or exclusion criteria, conduct of the study, patient management or patient assessment, and handling of the patient's rights will be described.

4.4.3.2 Protocol Deviations with PK Implications

Protocol deviations that may potentially impact PK parameter derivations include, but are not limited to:

- Emetic episode in case of orally administered study drug
- Missed PK samples that impact estimation of PK parameter(s)
- Concomitant medications not authorized by protocol
- PK samples obtained out of allowance window that may impact the estimation of PK parameter(s)
- Food intake deviations (not completely consumed or consumed outside of time allowed)

Protocol deviations (mentioned in Sections 4.4.3.1 and 4.4.3.2) and analysis population will be reviewed in the blinded data review meeting (BDRM) to decide inclusion or exclusion of patient(s) from analyses sets. Decisions regarding the exclusion of patients and/or patient data from analyses will be made prior to database lock and will be documented and approved, however, exclusion of patients or individual PK parameters will be decided after database lock after review of the calculable PK parameters, and any PK data excluded from summary tables/plots will be appropriately commented upon in the PK Listings.

A by-patient listing of major and minor protocol deviations will be provided including patient identifier; exclusion from specific analysis sets; and protocol deviation classification, and protocol deviation description and exclusion from specific analysis sets.

Protocol deviations related to Covid-19 will be listed separately.

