Parameter **Guideline for Derivation** C_{max}, t_{max}, C_{trough}, Obtained directly from the observed concentration-time data. If multiple t_{max} values are observed the earliest value will be reported. AUC_{0-t} The AUC from zero time (pre-dose) to the time of last quantifiable concentration will be calculated by the linear trapezoidal linear interpolation rule. The AUC_{0-t} is the sum of areas up to the time of the last quantifiable sample: $AUC_{0-t} = \int_0^t C_{last} * dt$ where C_{last} is the last observed quantifiable concentration. AUC_{tau} The AUC over the dosing interval (24 hours) will be determined for multiple dose studies using the trapezoidal rule, as stated above. The area from zero time extrapolated to infinite time will be calculated as follows: AUC_{0-inf} $AUC_{0-inf} = AUC_{0-t} + \frac{C_{\text{last}}}{\lambda_z}$ where Clast is the last observed quantifiable concentration. The percentage of AUC_{0-inf} obtained by extrapolation will be calculated as follows: %AUCex $\% AUC_{ex} = \frac{AUC_{0.inf} - AUC_{0.inf}}{AUC_{0.inf}} \times 100 .$ The apparent terminal phase rate-constant (λz) will be estimated by linear 1. λz and $t^{1/2}$ regression of concentration versus time data presented in a log-linear scale. Data are primarily monotonically decreasing in magnitude and are 2. representative of the actual decline in the log concentration-time curve. Only those data points that are judged to describe the terminal log-linear 3. decline will be used in the regression. 4. A minimum number of three data points in the terminal phase will be used in calculating λz with the line of regression starting at any post-C_{max} data point (C_{max} should not be part of the regression slope). Lambda z (λ_z) and other λ_z -related parameters (i.e. t¹/₂, AUC_{0-inf}, CL/F, MRT_{0-inf}, and V_z/F) will be flagged in listings and excluded accordingly from summary tables and statistical analysis of PK parameters, if the adjusted correlation coefficient (R^2 adjusted) is <0.8, and/or the interval used to determine λz is <1.3 times the half-life and/or %AUC_{ex} is >30%, unless otherwise determined by PK Scientist's best knowledge and judgment or if

Table 4-1 Pharmacokinetic Parameter and Estimation

	instructed by the Sponsor.		
	6. The $t^{1/2}$ will be calculated as follows:		
	$t^{1/2} = \ln 2/\lambda z = 0.693/\lambda z$		
	7. Data points may be dropped from the linear regression if the PK Scientist		

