4.12.3 Statistical Analysis of Pharmacokinetic Parameters

* Assessment of Dose Proportionality

Power model is used for assessment of dose proportionality.

- Power model:
 - Power model using linear regression method:

Dose proportionality will be assessed for C_{max} , AUC _{tau}, AUC_{0-inf}, and AUC_{0-t} on Day 1 and Day 7 using the PKAS who received single or multiple doses of TCK-276. PK parameters will be used to perform a LS linear regression analysis, using the formula ln_pkvar=A× ln_dose + B, where 'ln pkvar' represents the natural log transformed C_{max} AUC_{tau}, AUC_{0-inf}, and AUC_{0-t} parameters and 'ln_dose' represents the natural log-transformed dose. An estimate of the slope and intercept of the regression line and corresponding 95% CI will be obtained.

The following SAS code will be used:

ODS OUTPUT parameterestimates=est FitStatistics=fit;

PROC REG DATA = PP ALPHA=0.05 PLOTS=ALL;

BY PARAMCD PARAM;

MODEL LNAVAL=LNDOS/CLB;

RUN;

where:

LNAVAL: natural log-transformed PK parameter

LNDOS: natural log-transformed dose level of <drug>

PARAM: PK parameter

If the 95% confidence interval (CI) range for the slope includes 1 and the lack of fit test is not significant (*p*-value < 0.05), the relationship between dose and the PK parameter will be concluded to be dose proportional for the dose range studied.

If the 95% CI range for the slope does not include 1 or the lack of fit test is significant (*p*-value < 0.05), then additional dose proportionality assessments using above power model with narrower dose range will be performed by sequentially decreasing the number of doses either from higher or lower end of dose range studied as shown in below tabular manner for the respective assessments and combinations. The doses for the assessments must be sequential and include at least 3 doses. All the possible combinations of sequential ascending doses in a certain number of doses will be applied for the assessments. The additional proportionality assessments will be repeated until dose proportionality is found in any dose ranges (minimum 3 doses) and the lack of fit test is not significant.

Round	Combination	Range of Doses	Assessment	
		(in mg)		
1 st	With all four-dose studied	10, 25, 75, 175	If no dose proportionality is shown, perform 2nd Round	
2nd	1^{st} – with 3 doses	10, 25, 75	Stop the assessment at this round	
	2^{nd} – with 3 doses	25, 75, 175	even if none of the combinations shows dose proportionality.	
1			1	

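### SAP 4.4.3.2 lets patients or PK parameters be excluded after database lock, once values are known, with no criterion and no all-values dose-proportionality analysis

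*SAP*

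**What the plan says.** SAP 4.4.3.2 sends protocol deviations and analysis populations to a blinded data review meeting. Its general rule is: "Decisions regarding the exclusion of patients and/or patient data from analyses will be made prior to database lock and will be documented and approved". The same sentence then makes an exception for pharmacokinetics: "exclusion of patients or individual PK parameters will be decided after database lock after review of the calculable PK parameters". Data left out of tables or plots are to be commented on in the PK listings. The list of relevant deviations is open-ended: "Protocol deviations that may potentially impact PK parameter derivations include, but are not limited to" five examples. The PK population in SAP 4.4.1 requires only one quantifiable concentration and carries no exclusion condition.

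SAP 4.12.2, Table 4-1, gives numeric criteria for λz and the parameters that depend on it (t½, AUC0-inf, CL/F, MRT0-inf, Vz/F). These fail if adjusted R² is below 0.8, the fitted interval is shorter than 1.3 half-lives, or extrapolated AUC exceeds 30%. Failing values are "flagged in listings and excluded accordingly from summary tables and statistical analysis of PK parameters", "unless otherwise determined by PK Scientist's best knowledge and judgment or if" "instructed by the Sponsor". The listing rules in 4.12.2 require each flag or exclusion to be footnoted with its reason.

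SAP 4.12.3 fits a power model to Cmax, AUCtau, AUC0-inf and AUC0-t on Days 1 and 7. If the 95% CI for the slope contains 1 and lack of fit is not significant, "the relationship between dose and the PK parameter will be concluded to be dose proportional for the dose range studied". Otherwise the fit is repeated on three-dose subsets. No fit on all calculable values is planned beside the main one.

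**The concern.** Reviewing λz fits after non-compartmental analysis is normal, because a poor terminal fit cannot be seen before it is made. The exception in 4.4.3.2 is wider than that. It covers whole patients and any parameter, and the decision comes after the values have been reviewed. The pre-lock rule asks for documentation and approval. The post-lock exception states no criterion, decision-maker or approval step.

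The exposure differs by parameter. For Cmax, AUCtau and AUC0-t no numeric rule says when a value is unfit, so the 4.4.3.2 exception alone governs them. For AUC0-inf there is a numeric rule, but Table 4-1 allows it to be set aside with no condition stated.

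Exclusions feed a yes/no conclusion drawn from a small sample. The report would give one answer, without the answer that all values would have given.

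**Working it through.** **Inputs from the documents.** Each of four cohorts has 6 active and 2 placebo patients, so there are 4 × 6 = 24 active values at most per parameter and day. Doses are 10, 25 and 75 mg plus a top dose given as 175 mg in the SAP and 150 mg in the protocol. Those passages must be reconciled; both values were run. The interval is a two-sided 95% CI.

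**Assumed, because the documents do not give them.** Log-normal between-patient variation, CV 20 to 60%, no dropout, and a range of true slopes. One slope is suggested by the geometric mean AUC0-inf values from the single-dose study in protocol 2.2.2: ln(2,260/39.7)/ln(185/5) = 4.042/3.611 = 1.12. It uses only the two extreme doses, in healthy subjects on capsules.

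**Rule coded.** Least squares of ln(parameter) on ln(dose). The result is proportional if the slope CI (t, N − 2 df) contains 1 and the lack-of-fit F test (2, N − 4 df) has p ≥ 0.05. The SAP prints p < 0.05 beside its words for a non-significant test; it is read here as p ≥ 0.05. The second-round subset fits were not simulated.

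**Precision with all 24 values.** Half-width = t(0.975, 22) × σ/√Sxx, with σ² = ln(1 + CV²) and Sxx = 28.2 (175 mg top dose). At CV 40%: 2.074 × 0.385/5.31 = 0.150. At CV 20%, 30% and 60% it is 0.077, 0.115 and 0.217. One value at either end of the dose range can move the slope by a material part of this.

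**Constructed example, CV 40%, 175 mg top dose.**
- All 24 values: slope 1.150 (1.007 to 1.293), not proportional. Without the lowest 10 mg value: 1.119 (0.974 to 1.263), proportional.
- All 24 values: slope 1.130 (0.987 to 1.273), proportional. Without the highest 10 mg value: 1.161 (1.017 to 1.306), not proportional.

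Lack of fit is not significant in any of the four fits.

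**Simulation 1: CV 25% and 35%, top dose 150 or 175 mg.** Share of trials in which at least one of the 24 single exclusions reverses the conclusion:

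| True slope | CI criterion alone | Full rule with lack of fit |
|---|---|---|
| 1.00 | about 11–14% | about 23–28% |
| 1.12 | about 29–37% | about 34–43% |

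Under the full rule, one patient removed at random reverses it in about 3 to 8%.

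**Simulation 2: full rule, 175 mg top dose, 2,500 trials per cell** (Monte Carlo standard error at most √(0.25/2,500) = 1 percentage point). Same quantity, %:

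| CV | slope 1.00 | 1.05 | 1.10 | 1.20 |
|---|---|---|---|---|
| 20% | 26.4 | 36.1 | 32.0 | 0.5 |
| 30% | 26.6 | 33.4 | 40.4 | 12.8 |
| 40% | 25.0 | 28.5 | 38.6 | 29.5 |
| 60% | 26.0 | 27.1 | 33.2 | 40.3 |

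For slopes 1.00 to 1.10, some pair of exclusions reverses the conclusion in 54 to 69% of trials, and a random single exclusion in about 4 to 7%. Reversals run both ways: one exclusion can turn 22 to 67% of non-proportional results proportional, and 22 to 58% of proportional results non-proportional. With 150 mg on top and CV 40%, the single-exclusion figures are 27% (slope 1.0) and 38% (slope 1.1).

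**The case against.** A reader might infer that the Sponsor can order patients or values out of the analysis. The documents do not say so. The Sponsor wording appears only in Table 4-1, as an exception to a prespecified exclusion, so its natural effect is to keep a value that fails the criteria. It covers λz-related parameters only and never patients. AUC0-inf is the only such parameter in the power model, and the protocol's own analysis (9.3.3.1) uses only Cmax and AUCtau.

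A reader might also infer that exclusions are unchecked or hidden. They are not. A blinded review comes before lock, and deviations are predefined in a separate specification that is not available here. Exclusions are flagged with reasons, and PK parameters are listed by patient. Someone with the listings could refit the regression.

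The percentages should not be read as the chance that the trial reaches a reversed conclusion. They allow a free choice among 24 patients; sensitivity to one point is a property of small samples and is no evidence of misuse.

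Finally, little hangs on the result. There is no formal hypothesis, sample size rests on feasibility, and dose proportionality belongs to the secondary PK analysis. Escalation relies on safety data and AUCtau against a cap (protocol 7.1.2), not on the power model.

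All of this stands, and it limits the size of the point. It does not supply a criterion for post-lock exclusion of a patient or of a Cmax, AUCtau or AUC0-t value. Nor does it put the all-values result in the report.

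**Conclusion.** The point holds in a bounded form. SAP 4.4.3.2 sets a pre-lock rule and then exempts PK exclusions from it, after the values are known and without a criterion or decision-maker. Table 4-1 separately leaves the waiver of its λz criteria undefined, which matters for AUC0-inf.

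Some single exclusion would reverse the full-rule conclusion in roughly 23 to 43% of simulated trials, against about 3 to 8% for a random one. This rests on assumed CVs of 25 to 35%, true slopes of 1.00 to 1.12, log-normal variation and 24 complete values. It depends on the slope: at 1.20 with CV 20% it falls to 0.5%.

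The documents support a finding that the conclusion can depend on an unspecified later choice. They do not support a finding that such a choice will be made or that the Sponsor directs it. This is a cheap improvement to a secondary, descriptive analysis.

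**What to change.** 1. In SAP 4.4.3.2, limit post-lock exclusions to parameters that fail the Table 4-1 numeric criteria, or to deviations already recorded at the blinded data review meeting. Name who decides, and extend the documentation and approval step to these decisions.
2. In Table 4-1, replace both waivers (PK scientist's judgement and Sponsor instruction) with stated criteria, or delete both. Removing only the Sponsor words would leave the judgement waiver open.
3. In SAP 4.12.3, add the power model on all calculable values as a sensitivity analysis, reported beside the main fit for each parameter and day.

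The cost is a few sentences of SAP text and one repeated regression. No patient, sample or visit changes. The downside is slightly less freedom to remove odd profiles from the main table.
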